#### 8.5.1.3 Reduction in Palpable Spleen Length

Rate of reduction in palpable spleen length is defined as the proportion of subjects who achieved at least 50% reduction from baseline in palpable spleen length any time during the study.

Subjects who had baseline spleen length of greater than 0 > 0 will be included in this endpoint. Subjects who don't have post baseline spleen length will be excluded from this endpoint. Data after start of post-study treatment or disease progression will not be included in the analyses.

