- A spleen volume increase of $\geq 25\%$ (as assessed by MRI or CT scan) in iv. subjects with a spleen volume assessment prior to the initiation of ruxolitinib.
- c. Prior or current treatment with ruxolitinib for ≥ 28 days with intolerance defined as new RBC transfusion requirement (at least 2 units/month for 2 months) while receiving a total daily ruxolitinib dose of \geq 30 mg but unable to reduce dose further due to lack of efficacy.
- 9. Cohort 1b only: Subjects that are receiving ruxolitinib at the time of screening, must currently be on a stable dose ≥ 10 mg twice daily of ruxolitinib for ≥ 4 weeks prior to the 1st dose of navitoclax.
 - *Note:* Subjects with ruxolitinib dose reductions within 4 weeks prior to study enrollment are considered to be on stable dose if dose of ruxolitinib is unchanged for ≥ 2 weeks prior to Day 1 of navitoclax. The current dose must be ≥ 10 mg twice daily. If the dose reduction was due to thrombocytopenia, platelet counts must be confirmed to be stable by a repeat laboratory test.
- 10. **Cohort 1b only:** Subject must not have received treatment with a BET inhibitor or an alternate JAK-2 inhibitor other than ruxolitinib.
- Cohort 2 only: Subject must have received prior treatment with JAK-2 inhibitor 11. therapy and meet one of the following criteria (a or b):
 - a. Prior treatment with JAK-2 inhibitor for at least 12 weeks
 - b. Prior treatment with JAK-2 inhibitor for ≥ 28 days complicated by any of the following:
 - Development of red blood cell transfusion requirement (at least 2 units/month for 2 months OR
 - Grade ≥ 3 adverse events of thrombocytopenia, anemia, hematoma and/or hemorrhage while on JAK-2 inhibitor treatment

- 12. **Cohort 3 only:** Subject must not have received prior treatment with a JAK-2 or BET inhibitor.
- Subject has splenomegaly defined as a spleen palpation measurement ≥ 5 cm below 13. costal margin or spleen volume $\geq 450 \text{ cm}^3$ as assessed by MRI/CT.
- 14. Cohorts 1b and 3 only: Subject has at least 2 symptoms each with a score \geq 3 or a total score of \geq 12, as measured by the MFSAF v4.0 on at least 4 out of 7 days during screening prior to study drug dosing.
- 15. Subject must meet the following laboratory parameters per local laboratory reference range during screening, prior to study drug dosing:
 - Adequate bone marrow reserve; in the absence of growth factors, thrombopoietic factors, or platelet transfusions for at least 14 days:

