5.3.2.2 Handling/Processing of Samples

Blood Samples for Navitoclax PK Assay (All Cohorts)

Detailed sample collection and processing instructions for the navitoclax PK will be provided in the current Study M16-109 laboratory manual.

Blood Samples for Ruxolitinib PK Assay (Cohorts 1a, 1b and 3)

Detailed sample collection and processing instructions for the ruxolitinib PK will be provided in the current Study M16-109 laboratory manual.

5.3.2.3 **Disposition of Samples**

The frozen plasma PK samples for navitoclax and possible metabolite(s) assay and frozen plasma samples for PK samples for ruxolitinib assay will be packed in dry ice sufficient to last during transport and shipped from the study site to a central lab designated by AbbVie. An inventory of the samples included will accompany the package. Please refer to current Study M16-109 laboratory manual for complete shipping instructions.

5.3.2.4 **Measurement Methods**

Plasma concentrations of navitoclax will be determined by the Bioanalysis Department at AbbVie using a validated method. Plasma concentration of possible navitoclax metabolite(s) may be determined with validated or non-validated methods.

Plasma concentration of ruxolitinib will be determined under the supervision of the Bioanalysis Department at AbbVie.

5.3.3 **Efficacy Endpoints**

Primary Endpoints

The primary efficacy endpoint is at least 35% reduction from baseline in spleen volume at Week 24 (SVR_{35W24}) as measured by MRI/CT.

Secondary Endpoints

Secondary efficacy endpoints are as follows:

- At least 50% reduction in TSS at Week 24 from baseline as measured by MFSAF version 4.0
- The anemia response
- Change in grade of the bone marrow fibrosis according to the European consensus grading system³⁶ (Appendix F)

Exploratory Endpoints

Exploratory efficacy endpoints may include, but are not limited to:

- At least 35% reduction in spleen volume from baseline (SVR₃₅) as measured by MRI or CT scan, per modified IWG criteria at any time point during study
- Duration of SVR₃₅
- At least 50% reduction in palpable splenomegaly from baseline per modified IWG criteria
- At least 50% reduction in TSS at any time point from baseline as measured by MFSAF v4.0
- Change from baseline in TSS
- Red blood cell transfusion during study treatment
- Duration of anemia response
- Exploratory analyses of the MFSAF v4.0, PROMIS Fatigue SF 7a, and EORTC QLQ-C30
- Overall response per modified IWG criteria
- PFS per modified IWG criteria
- OS

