Appendix E. Modified IWG-MRT/ELN Response Criteria for Myelofibrosis

Table 9. Summary of Response Criteria

		nents (for all response categori							
Response	for	$r \ge 12$ wk to qualify as a respon	ise)						
Category	Bone Marrow	Peripheral Blood	Clinical						
Complete Remission (CR)	 Age-adjusted normocellularity < 5% blasts Grade ≤ 1 MF (Appendix F) 	 Hgb ≥ 10g/dL Neutrophils ≥ 1 × 10⁹/L Platelets ≥ 100 × 10⁹/L < 2% immature myeloid cells 	 Resolution of disease symptoms Spleen/Liver not palpable No evidence of EMH 						
Partial Remission (PR)	Not Applicable	 Hgb ≥ 10 g/dL Neutrophils ≥ 1 × 10⁹/L Platelets ≥ 100 × 10⁹/L < 2% immature myeloid cells 	 Resolution of disease symptoms Spleen/Liver not palpable No evidence of EMH 						
		OR							
	 Age-adjusted normocellularity < 5% blasts Grade ≤ 1 MF (Appendix F) 	 Hgb ≥ 8.5 g/dL Neutrophils ≥ 1 × 10⁹/L Platelets ≥ 50 × 10⁹/L < 2% immature myeloid cells 	 Resolution of disease symptoms Spleen/Liver not palpable No evidence of EMH 						
Clinical Improvement		pleen or symptom response with thrombocytopenia or neutropeni							
Anemia Response	•	eline Hgb < 10 g/dL): Hgb incre ning transfusion independent**	ase $\geq 2 \text{ g/dL}$						
Spleen Response	A baseline splenomegaly that is palpable at $5-10$ cm below the LCM, becomes not palpable*** A baseline splenomegaly that is palpable at >10 cm below the LCM, decreases by $\geq 50\%$ *** MRI/CT showing $\geq 35\%$ SVR								
Symptoms Response	≥ 50% reduction in MF-SAF T	TSS							
Stable Disease	Belonging to none of the above	e response categories							

EMH = extramedullary hematopoiesis; LCM = left costal margin

^{*} Increase in severity of anemia constitutes the occurrence of new transfusion dependency or a ≥ 2 g/dL decrease in Hgb from pretreatment baseline that lasts for ≥ 12 weeks. Increase in severity of thrombocytopenia or neutropenia is defined as a 2-grade decline, from pretreatment baseline, in platelet count or ANC. In addition, assignment to Clinical Improvement requires a minimum platelet count of ≥ 25 × 10⁹/L and ANC ≥ 0.5 × 10⁹/L.

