^{**} Transfusion dependency before study enrollment is defined as transfusions of at least 6 units of packed red blood cells (PRBC), in the 12 weeks prior to study enrollment. In addition, the most recent transfusion episode must have occurred in the 28 days prior to study enrollment. Response in transfusion-dependent patients requires absence of any PRBC transfusions during any consecutive "rolling" 12-week interval during the treatment phase.

^{***} Requires confirmation by MRI/CT with a \geq 35% SVR.

[figure not shown]

Table 10. Summary of Cytogenetic Remission

Cytogenetic Remission Category	Cytogenetic Remission Requirements At least 10 metaphases must be analyzed
	Requires confirmation by repeat testing within 6 months
Complete Cytogenetic Remission	Eradication of a preexisting abnormality
Partial Cytogenetic Remission	\geq 50% reduction in abnormal metaphases (to qualify for PR: must have \geq 10 abnormal metaphases at baseline)

Table 11. Summary of Molecular Remission

Molecular Remission	Molecular Remission Requirements		
Category	Must be analyzed in peripheral blood granulocytes		
	Requires confirmation by repeat testing within 6 months		
Complete Molecular Remission	Eradication of a pre-existing abnormality		
Partial Molecular Remission	\geq 50% decrease in allele burden (to qualify for PR: must have \geq 20% mutant allele burden at baseling		

[figure not shown]

Table 12. Summary of Progression/Relapse Criteria

Progression/Relapse Category	Progression/Relapse Criteria		
Progressive Disease	At least 1 of the following:		
	• Appearance of a new splenomegaly that is palpable at least 5 cm below the left costal margin (LCM)*		
	• A \geq 100% increase in palpable distance below LCM, for baseline splenomegaly of 5 – 10 cm*		
	• A 50% increase in palpable distance below LCM, for baseline splenomegaly of > 10 cm*		
	• MRI/CT showing a \geq 25% increase in spleen volume from baseline		
	• Leukemic transformation confirmed by a bone marrow blast count of ≥ 20%		
	• A peripheral blood blast content of $\geq 20\%$ associated with an absolute blast count of $\geq 1 \times 10^9/L$ that lasts for at least 2 weeks		
Relapse	At least 1 of the following:		
	No longer meeting criteria for at least Clinical Improvement after achieving Complete Response, Partial Response or Clinical Improvement		
	• Loss of anemia response persisting for ≥ 1 month		
	• Loss of spleen response persisting for ≥ 1 month		

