# 3.3 Additional Efficacy Endpoint(s)

Exploratory efficacy endpoints are as follows:

- SVR35, at least 35% reduction in spleen volume from baseline as measured by MRI or CT according to the IWG criteria at any time point during study
- Duration of SVR35
- At least 50% reduction in palpable spleen length from baseline
- At least 50% reduction in TSS at any time point from baseline as measured by MFSAF v4.0

- Change in TSS and each MFSAF (v4.0) score from baseline
- Duration of anemia response
- Change in EORTC-QLQ-C30 score from baseline
- Change in PROMIS score from baseline
- Overall response per modified IWG criteria
- Progression Free Survival (PFS) per modified IWG criteria
- Overall survival (OS)
- 10%, 20%, and 30% Reduction in spleen volume from baseline as measured (SVR10, SVR20, and SVR30) by MRI/CT at any time point during study
- 10%, 20%, and 30% Reduction in spleen volume from baseline as measured (SVR10, SVR20, and SVR30) by MRI/CT at Week 24
- Post-baseline PRBC transfusion independence

[figure not shown]

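### The SAP scores palpable spleen response as one 50% fall from any baseline above 0 cm, while the protocol ties it to modified IWG criteria that its own 50% wording does not match at 5–10 cm

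*SAP*

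**What the plan says.** Protocol 5.3.3 and 8.2.3 list the exploratory endpoint as "At least 50% reduction in palpable splenomegaly from baseline per modified IWG criteria".

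Protocol Appendix E, Table 9 sets out those criteria for the spleen. For a baseline of 5–10 cm, the spleen "cm below the LCM, becomes not palpable". The 50% threshold belongs to the next line only: "A baseline splenomegaly that is palpable at >10 cm below the LCM, decreases by" at least 50%. A footnote to both lines reads "Requires confirmation by MRI/CT with a" spleen volume reduction (SVR) of at least 35%. The table header, partly broken in the text available, asks for at least 12 weeks' duration in all response categories. No palpation route is given for a baseline below 5 cm.

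SAP 3.3 lists the endpoint as "At least 50% reduction in palpable spleen length from baseline", without the reference to IWG. SAP 8.5.1.3 counts subjects who "achieved at least 50% reduction from baseline in palpable spleen length any time during the study". It includes every baseline above 0 cm and drops data after progression or post-study treatment. It has no size strata, imaging confirmation or duration. SAP Appendix B reprints the spleen strata and the MRI confirmation, but 8.5.1.3 does not refer to it.

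**The concern.** A reader who knows the protocol will take the reported figure for an IWG-type palpation response, and it is not one. The SAP's introduction says that it elaborates the protocol's methods. Here it changes the criterion without giving a reason, although the same list in SAP 3.3 keeps the modified IWG reference for overall response and PFS. The version history mentions spleen length only for missing data.

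The SAP rule is also sensitive to reading error. Palpation is done at every clinic visit of an open-label study, and the best single reading decides. When the baseline is small, 1 cm of error can be a 50% fall. Small baselines are possible because inclusion criterion 13, which begins "Subject has splenomegaly defined as a spleen palpation measurement" of at least 5 cm, also accepts a spleen volume of at least 450 cm³ instead. What is at stake is an exploratory rate that answers a different question from the protocol's and errs upward.

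**Working it through.** The documents give no rate or precision figure for this endpoint, so there is none to reproduce.

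**Step 1. Both rules on the same readings.** Fall = (baseline − follow-up) / baseline.

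| Baseline → follow-up (cm) | Fall | SAP 8.5.1.3 | Table 9, palpation part |
|---|---|---|---|
| 2 → 1 | 50% | responder | no route below 5 cm |
| 4 → 2 | 50% | responder | no route below 5 cm |
| 8 → 4 | 50% | responder | no, still palpable |
| 10 → 5 | 50% | responder | no, still palpable |
| 10 → 0 | 100% | responder | met, if SVR ≥ 35% and ≥ 12 weeks |
| 12 → 6 | 50% | responder | met, if SVR ≥ 35% and ≥ 12 weeks |

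This step needs no assumption about reading error. The 8 → 4 and 10 → 5 rows meet the protocol bullet's literal 50% but fail Table 9, so the protocol disagrees with itself at 5–10 cm.

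**Step 2. An unchanged spleen under the SAP rule.**

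From the documents: palpation at Weeks 1, 2, 3, 4, 6, 8, 12, 16, 20 and 24 (10 exams), then every 12 weeks, so 12 exams by Week 48.

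Assumed, not in the documents: normal reading error with SD 0.5, 1.0 or 1.5 cm, independent between exams; readings rounded to whole cm and floored at 0; all 12 exams retained.

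Let p(b) be the probability of baseline reading b, and q(b) the probability that one follow-up reading is at most b/2. Then

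P(responder) = Σ p(b) · [1 − (1 − q(b))¹²] / Σ p(b), summed over b ≥ 1.

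Example, true 2 cm, SD 1.0:
- p(1) = 0.242, p(2) = 0.383, p(3) = 0.242, p(4 or more) = 0.067, p(0) = 0.067.
- q(1) = 0.067, giving 1 − 0.933¹² = 0.564.
- q(2) = q(3) = 0.309, giving 1 − 0.691¹² = 0.988.
- For b ≥ 4, q is at least 0.691, giving about 1.
- Sum: 0.242 × 0.564 + 0.625 × 0.988 + 0.067 = 0.820. Divided by 0.933, this is 0.879.

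| True length (cm) | SD 0.5 | SD 1.0 | SD 1.5 |
|---|---|---|---|
| 2 | 74% | 88% | 97% |
| 3 | 15% | 67% | 87% |
| 4 | 1% | 44% | 72% |
| 5 | 0.3% | 22% | 56% |
| 6 | 0% | 8% | 39% |
| 8 | 0% | 0.7% | 13% |
| 12 | 0% | 0% | 0.4% |

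With only the 10 exams to Week 24, the figures are 70%, 85% and 95% at 2 cm, and 0.2%, 20% and 51% at 5 cm. Using the Week 24 exam alone at 2 cm gives 13%, 27% and 37%, so much of the excess comes from taking the best of many readings.

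**Step 3. Is a 5 cm floor enough?** Repeat the sum over b ≥ 5 only. At a true 5 cm it gives 0.3%, 30% and 71%. The floor selects high baseline readings, so chance falls remain common.

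Now also require the 50% fall at two consecutive exams. With N₀ = N₁ = 1 and Nₖ = (1 − q)Nₖ₋₁ + q(1 − q)Nₖ₋₂, replace the bracket by 1 − N₁₂. At a true 5 cm this gives 0%, 3% and 18%; at 6 cm, 0%, 0.4% and 6%. The floor needs the repeat reading.

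**The case against.** The best case for the SAP is that it followed the number in the protocol's bullet. That bullet is a flat 50%, which fits Table 9 only above 10 cm. A reader might infer that the SAP broke a clear protocol rule. The documents do not support that, because the protocol is itself inconsistent and both texts need repair. But the flat 50% does not explain a floor of 0 cm or the loss of the IWG reference, confirmation and duration.

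Scoring by Table 9 in full also has a cost. Its imaging footnote means that every palpation responder already has an SVR of at least 35%. Such responders are a subset of the any-time SVR35 responders that SAP 8.5.1.1 reports, so little independent information is left. This stands, and it is why a separate palpation summary is a legitimate alternative.

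The endpoint is exploratory, without formal testing, and no decision rests on it. The SAP titles it as a reduction in palpable length, not as an IWG response. Scoring at any time matches neighbouring exploratory endpoints. All of this limits the consequence.

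Finally, the probabilities rest on an assumed reading SD, independent errors and full retention to Week 48, while the SAP drops data after progression or post-study treatment. This also stands, and the results are therefore shown as ranges.

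**Conclusion.** The mismatch is real. As written, SAP 8.5.1.3 gives a different rate from the one the protocol describes, with an upward bias, because a single favourable reading from any non-zero baseline is enough. For an unchanged spleen the false-response probability is 74–97% at 2 cm, 0–56% at 5 cm, 0–13% at 8 cm and under 1% at 12 cm, under the assumptions listed. The reclassification of 8 → 4 cm depends on none of them.

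Two stronger readings are tempting. One is that a cohort's palpation rate will be grossly inflated, or will look far better than centrally read SVR35. The documents give no distribution of baseline palpable length, so the effect on any cohort's rate is unknown. Criterion 13 permits baselines under 5 cm but does not show how many, if any, will enrol. The other is that the trial's main result is affected. It is not: the primary endpoint is SVR35 at Week 24 from centrally reviewed imaging.

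**What to change.** Reconcile the bullet in Protocol 5.3.3 and 8.2.3, Protocol Table 9, and SAP 3.3 and 8.5.1.3. Either of two routes would do.

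(a) Score the endpoint by Table 9 in full: baseline of at least 5 cm, the size strata, confirmation by MRI/CT with an SVR of at least 35%, and at least 12 weeks' duration. State which scan confirms which palpation and how duration is judged across visits. Note that responders are then a subset of the any-time SVR35 responders. Cite Protocol Table 9, since the 12-week header does not appear in the available text of SAP Table B-1.

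(b) Keep the 50% rate as a separate palpation summary. Limit it to baselines of at least 5 cm, require the reduction to be sustained at consecutive visits, and label it as not the IWG spleen response. Specify the number of visits or a minimum interval, because the first four scheduled exams are a week apart.

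The cost is wording in both documents and one derivation from palpation and imaging data already collected. The downside is a smaller denominator and, most likely, a lower reported rate.

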# 8.0 Efficacy Analyses

#### 8.1 General Considerations

The primary analysis population for primary endpoint is the Full Analysis Set. Unless otherwise specified, the secondary efficacy endpoints and exploratory efficacy endpoints will be analyzed in Full Analysis Set.

All efficacy results will be presented by cohort unless stated otherwise. For all analyses, unless otherwise specified, data collected after the cutoff date will be excluded from statistical analysis. All spleen volume related endpoints described in Section 3.0 will be based on the assessments from the central review of the radiographic images by an Independent Review Committee (IRC) as described in the protocol.

abbyie Navitoclax/ABT-263

Navitoclax/ABT-263 M16-109 – Statistical Analysis Plan Version 4.0 – 31 January 2023

All response rates and the corresponding 95% confidence interval (Cl) using the Clopper-Pearson method will be provided.

For the analyses of all time-to-event endpoints, survivorship functions will be estimated using Kaplan-Meier product-limit methodology. If reached, median time-to-event and its 95% CI will be presented.

For the analyses of all continuous endpoints, such as change from baseline in score, the scores will be summarized with baseline mean, visit mean, mean change from baseline, mean percentage change from baseline, standard deviation, and the corresponding 95% CIs.

Baseline measurement related to each efficacy endpoint for analysis has been described in Section 7.0.

[figure not shown]
The post-study treatment refers to Post Study Drug Systemic Therapies for Myelofibrosis, Post Study Drug Radiation Therapy and Post Study Drug Transplant. The disease progression (DP) refers to relapse or progressive disease in the Disease Response Assessment Form.

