# 8.2 Handling of Missing Data

Missing data for all time-to-event endpoints will be handled by appropriate censoring in analysis and the censoring rule will be described in the following sub-sections.

Unless otherwise specified, for the analyses of all response rates, subjects without response will be considered as non-responders.

No missing data imputation will be applied for change from baseline in PRO domain score.

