#### 8.5 Exploratory Efficacy Analyses

#### 8.5.1 Exploratory Efficacy Endpoints

8.5.1.1 Spleen Volume Reduction  $\geq$  10%,  $\geq$  20%, 30%, and  $\geq$  35% at Any Time (SVR10, SVR20, SVR30 and SVR35), Spleen Volume Reduction  $\geq$  10%,  $\geq$  20%, and  $\geq$  30% at Week 24

SVR10, SVR20, SVR30, and SVR35 rates at any time are defined as the proportion of subjects who achieved at least 10%, 20%, 30%, and 35% reduction from baseline spleen volume any time, respectively. SVR10, SVR20, and SVR30 at Week 24 are defined as the proportion of subjects who achieved at least 10%, 20%, and 30% reduction from baseline spleen volume at Week 24, respectively. Data after the start of post-study treatment or disease progression will be excluded from these analyses. Subjects who do not have

percent change from baseline (missing baseline or missing post-baseline) in spleen volume will be treated as non-responders. In addition, time to first SVR  $\geq$  10%, first SVR  $\geq$  20%, first SVR  $\geq$  30%, and first SVR  $\geq$  35% will also be summarized.

Above exploratory endpoints will be analyzed in the Full Analysis Set.

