## 8.5.1.4 TSS Reduction $\geq$ 50% (TSS50)

TSS50 rate is defined as the proportion of subjects who achieved at least 50% reduction from baseline in TSS at any week during the study.

Subjects who do not have any post baseline TSS score will be treated as non-responders. Subjects with baseline TSS of 0 or without baseline TSS score will also considered as non-responders. Data after the start of post-study treatment or disease progression will not be included in the analyses.

TSS50 rate will be analyzed in the Full Analysis Set.

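### The palpable spleen response rate leaves out subjects with no usable post-baseline palpation, an unexplained exception that can only raise the rate, though probably by little

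*SAP*

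**What the plan says.** SAP 8.5.1.3 gives the rate as the proportion of subjects who "achieved at least 50% reduction from baseline in palpable spleen length any time during the study". It limits the endpoint to subjects whose baseline length is above 0. It then adds two rules about post-baseline data:

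- "Subjects who don't have post baseline spleen length will be excluded from this endpoint"
- Values obtained once post-study treatment has begun, or once the disease has progressed, are set aside.

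Elsewhere the SAP handles missing data differently:

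- The default in SAP 8.2, which opens with a clause allowing exceptions, is: "for the analyses of all response rates, subjects without response will be considered as non-responders".
- For the any-time spleen volume reductions (SAP 8.5.1.1), subjects without a "percent change from baseline (missing baseline or missing post-baseline) in spleen volume will be treated as non-responders".
- For the any-time symptom response (SAP 8.5.1.4): "Subjects who do not have any post baseline TSS score will be treated as non-responders".
- On the population (SAP 8.1): "Unless otherwise specified, the secondary efficacy endpoints and exploratory efficacy endpoints will be analyzed in Full Analysis Set". SAP 4.0 admits to that set every enrolled subject who took at least one dose of navitoclax.

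SAP 8.5.1.3 does not explain its different rule. Neither document plans a sensitivity analysis that counts the excluded subjects as non-responders.

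**The concern.** Whether a subject has any post-baseline palpation is known only after treatment starts. A denominator that depends on it is no longer fixed at baseline. The subjects it loses are mainly those lost or dead before any post-dose examination. It may also lose those whose only values come after progression or post-study treatment, since those values are set aside. None of these subjects can be in the numerator, and few would be expected to have done well. Taking them out of the denominator moves the rate in one direction only.

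What is at stake is modest. The endpoint is exploratory, and the primary endpoint (SAP 8.3.1) already counts missing spleen volume as non-response. Still, palpation is a second view of the spleen effect that the trial is built around, and its rate should not benefit from early loss.

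**Working it through.** **Inputs.** The documents give no palpation response rate, no count of subjects without a post-baseline palpation, and no count with baseline length above 0. For illustration I borrow x and n from SAP Table 1, which concerns a different endpoint (spleen volume reduction of at least 35% at Week 24). I assume that all n subjects have baseline length above 0 and that k = 1 to 3 lack a usable post-baseline value.

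**Reproducing the plan's figures.** Clopper-Pearson limits from beta quantiles match all 12 rows of SAP Table 1 to two decimals, for example:

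- 12/30 = 40.00% (22.66 to 59.40)
- 16/34 = 47.06% (29.78 to 64.87)
- 32/70 = 45.71% (33.74 to 58.06)

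**Formula.** The k subjects have no value that could qualify as a response, so x is the same under both rules.

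- Rate under SAP 8.5.1.3: x/(n-k)
- Rate with missing counted as non-response: x/n
- Ratio: n/(n-k), which is at least 1
- Difference: xk/[n(n-k)], which is zero if k = 0 or x = 0 and positive otherwise

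**Results.**

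| x, n | Non-responder rule | k = 1 | k = 2 | k = 3 | Rise at k = 3 |
|---|---|---|---|---|---|
| 12, 30 (Cohort 2 or 3) | 40.0% | 12/29 = 41.4% | 12/28 = 42.9% | 12/27 = 44.4% | 4.4 points |
| 16, 34 (Cohort 1a) | 47.1% | 16/33 = 48.5% | 16/32 = 50.0% | 16/31 = 51.6% | 4.6 points |
| 32, 70 (Cohort 1b) | 45.7% | 32/69 = 46.4% | 32/68 = 47.1% | 32/67 = 47.8% | 2.0 points |

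The exact interval moves up too. For 12 responders it goes from 22.7 to 59.4 (n = 30) to 25.5 to 64.7 (n = 27).

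**How large can k be?** Only a subject with no usable palpation at all is lost. The protocol synopsis schedules palpation at Weeks 1, 2, 3, 4, 6, 8, 12, 16, 20 and 24 and every 12 weeks after that. Protocol Appendix C, Table 6 also marks the examination at the treatment completion visit and the 30-day safety visit, and its footnote requires spleen palpation as a minimum. So k is probably small.

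It need not be zero. One dose puts a subject in the Full Analysis Set, a week before the first scheduled palpation. Protocol 5.3.1.1 lists palpation among activities done at the site during the pandemic, so it could be missed or delayed.

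**The case against.** The strongest reply is that the SAP is free to do this. The default in 8.2 allows exceptions, and 8.5.1.3 states one. It is not the only one: SAP 8.4.1.3 excludes missing grades from the bone marrow fibrosis reduction, a secondary endpoint. This stands. The rule is a permitted exception and does not contradict 8.2. Being permitted does not supply a reason for a denominator that depends on follow-up.

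The effect is also small beside the sampling error. The half-width in SAP Table 1 is 18.37 points at 12/30, against a shift of 4.4 points at k = 3. No formal test is planned (Protocol 8.3). This also stands, and it limits the weight of the point. But the shift always has the same sign, and a wide interval does not correct for it.

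A reader might infer more than the documents support:

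- **That early dropouts in general leave the denominator.** They do not. One usable palpation keeps a subject in, and without a 50% reduction that subject counts as a non-responder.
- **That stopping for thrombocytopenia drives the bias.** A subject who stops at Week 3 or Week 10 should already have several palpations, and an examination is due at treatment completion. The documents give no discontinuation figure that would support this reading.
- **That the fix would make the palpation and spleen volume rates directly comparable.** It would not. Palpation is limited to baseline length above 0, while the volume endpoints use the whole Full Analysis Set. Inclusion criterion 13 admits subjects on a volume of at least 450 cm³ alone, so some may have no palpable spleen. The measures differ as well: half of palpated length against 35% of centrally read volume.
- **That the SAP version history shows the sentence to be a mistake.** The log mentions aligning spleen length handling with spleen volume, but it describes changes between versions and is not evidence about the current text.

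**Conclusion.** The point holds as a minor one. The direction is certain: relative to the SAP's own default, the rule in 8.5.1.3 can raise the palpable spleen response rate and can never lower it. The size is unknown because x and k are not given for this endpoint. Under the borrowed inputs and k = 1 to 3, the rise is 1.4 to 4.6 points in cohorts of 30 to 34 and 0.7 to 2.0 points with n = 70. If fewer subjects have a palpable spleen at baseline, n is smaller and each exclusion weighs more.

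Limiting the endpoint to baseline length above 0 is a separate matter and is sound. A percentage reduction from 0 is undefined, and that restriction is fixed before treatment.

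**What to change.** Replace the exclusion sentence in SAP 8.5.1.3 with a rule that Full Analysis Set subjects with baseline palpable length above 0 and no usable post-baseline measurement count as non-responders. Define usable as obtained before the start of post-study treatment or disease progression, because the current text does not say how a subject with only later values is handled. Keep the restriction to baseline length above 0.

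If the sponsor prefers to exclude, the SAP should give the reason, and the report should show k and both rates.

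The cost is one SAP sentence and a small programming change, with no new data. The exploratory rate may come out slightly lower.
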